### 4.2 Scientific Rationale for Study Design

The primary objective of the study is to assess the safety and tolerability profiles of a 3-dose regimen of V160 administered IM in Japanese male participants 20 years to 64 years of age inclusive who are in good medical health at the start of the study. The selected population for this first study in Japanese participants is consistent with the population typically used in Phase I clinical studies, namely healthy adult male at low risk for disease, prior to include Japanese women of childbearing age in near future study. Considering possibility of future use in CMV seropositive population, this study will enroll CMV seropositive participants to collect safety and immunogenicity data as well as CMV seronegative ones. Approximately 18 participants will be enrolled in this study to include 9 CMV-seropositive and 9 CMV-seronegative individuals.

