## 9.1 Statistical Analysis Plan Summary

Key elements of the statistical analysis plan are summarized below; the comprehensive plan is provided in Sections 9.2-9.12.

Study Design Overview	A Phase I Randomized, Double-Blind, Placebo-controlled Study to Evaluate the Safety, Tolerability and Immunogenicity of V160 (Human Cytomegalovirus Vaccine) in Healthy Japanese Men
Intervention Assignment	Participants will be randomized in a 2:1 ratio to either V160 or Placebo, stratified by CMV serostatus.
Analysis Populations	Efficacy: Per Protocol Immunogenicity (PPI) population Safety: All participants as treated (APaT) population
Primary Endpoint	

Solicited injection site AEs within Days 1 through 5 after each vaccination visit

Solicited systemic AEs within Days 1 through 14 after each vaccination visit

Vaccine-related SAEs within Days 1 through 14 after each vaccination visit

Secondary Endpoint	

CMV-specific NAb titers at 1 month PD3

Viral detection of V160 in plasma, urine and saliva, and injection-site swab and adhesive tape swab

Statistical Methods for Key Efficacy Analyses	CMV-specific NAb GMT at 1 month PD3 will be analyzed for seronegative participants using analysis of variance (ANOVA) model. The model will include term for intervention. The GMT ratio and 95% confidence intervals (CIs) will be estimated from this model.
Statistical Methods for Key Safety Analyses	Incidence of solicited injection site AEs, solicited systemic AEs and vaccine-related SAEs will be summarized for each serostatus, respectively.
Interim Analyses	No interim analyses are planned in this study.
Multiplicity	No multiplicity adjustment is planned in this study.
Sample Size and Power	A total of 9 participants will be enrolled for each CMV serostatus. Assuming a discontinuation rate of approximately 20%, 7 participants are expected to complete intervention.

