### 9.3 Hypotheses/Estimation

There are no hypotheses for the study. Objectives are stated in Section 3.

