#### **9.6.2 Statistical Methods for Safety Analyses**

Safety and tolerability will be assessed by clinical review of all relevant parameters including AEs and vital signs. All participants who are vaccinated and eligible for inclusion in the APaT population as defined in Section 9.5.2 will be included in the safety analyses and summaries. Incidence of AEs will be summarized as frequencies and percentages by vaccination group.

To provide an overall assessment, safety measures such as the incidence of the following events occurring throughout the study will be summarized for each serostatus, respectively:

- 1) any AE,
- 2) any injection-site AE,
- 3) any systemic AE,
- 4) any SAE,
- 5) any vaccine-related SAE,
- 6) any discontinuation due to an AE within 14 days of receipt of any study vaccination

AEs will be summarized by vaccination visit and across all vaccination visits. Specific AEs for which summaries will be provided are identified in [Table 4](#).

- The number and percent of the participants with positive viral shedding in urine and saliva up to 1 month postdose 3 (defined by viral load in saliva/urine  $\geq$  assay defined threshold cutoff value) will be also summarized for generic CMV and for vaccine-type virus separately, by vaccination group by CMV serostatus.
- The number and percent of the participants with positive viral detection in plasma up to 14 days postdose 1 (defined by viral load in plasma  $\geq$  assay defined threshold cutoff value) will be also summarized for generic CMV and for vaccine-type virus separately, by vaccination group by CMV serostatus.
- The number and percent of the participants with positive viral leakage in injection-site swab and adhesive tape swab up to 30 minutes postdose 1 (defined by viral load in injection-site swab/adhesive tape swab  $\geq$  assay defined threshold cutoff value) will be also summarized for generic CMV by vaccination group by CMV serostatus.
- The oral temperatures recorded on the VRC will also be summarized.

Table 4 Safety Analyses of Adverse Events Endpoints

Adverse Events endpoints	Time Window		
	Day1 to Day 5 †	Day 1 to Day 14 †	Any Time during Study
-Solicited Injection site AEs of pain/tenderness, erythema/redness, and swelling	●		
-Unsolicited injection site AEs		●	
-Solicited systemic AEs of fatigue, myalgia, headache and arthralgia		●	
-Unsolicited systemic AEs		●	
-Serious AEs		●	
-VR SAEs		●	
- Discontinuation due to an AE		●	

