-Elevated temperature §		●	
-Death			●
-Any AE		●	
-Saliva/Urine viral Shedding*			●
-Viral detection from plasma*			●
-Viral leakage from swab sampling of injection-site/adhesive tape*			●

Summaries will be provided by vaccination group separately for the participants in each serostatus.

† The day of vaccination is counted as Day1. Day 1 to Day 5 refers to the day of vaccination plus 4 days immediately post-vaccination.  
Day 1 to Day 14 refers to the day of vaccination plus 13 days immediately post-vaccination.

\* The viral shedding, viral detection from plasma, and viral leakage data will be summarized as percentage of positivity by Visit; the duration for collecting viral shedding is shown in SoA.

§ Defined as  $\geq 38.0^{\circ}\text{C}$  oral or equivalent.

AE=Adverse Events, SAE=Serious Adverse Events, VR=Vaccine-Related.

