### **9.9 Sample Size and Power Calculations**

Nine participants will be randomized in a ratio of 2:1 into V160 and placebo for each CMV serostatus cohort.

If a specific AE is not observed in any of the 6 participants in V160, then the true incidence of that event is 46% or less with 90% confidence.

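### Primary adverse-event incidences are planned as counts and percentages in cells of 6 and 3, with no confidence intervals and no clearly specified pooled V160 summary

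*Combined protocol and SAP*

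**What the plan says.** Section 3 sets the primary objective as safety and tolerability by CMV serostatus, and Section 9.3 states: "There are no hypotheses for the study. Objectives are stated in Section 3".

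The statistic planned for adverse events is in Section 9.6.2: "Incidence of AEs will be summarized as frequencies and percentages by vaccination group". That sentence does not mention serostatus. Three other places do: the key safety methods row of Section 9.1, the overall-assessment list in Section 9.6.2, and the note under Table 4, which reads "Summaries will be provided by vaccination group separately for the participants in each serostatus".

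The only interval planned anywhere in Section 9 is the 95% interval for the neutralizing antibody GMT ratio in seronegative participants, a secondary endpoint (Sections 9.1 and 9.6.1). The supplemental SAP is mentioned for later changes (opening of Section 9) and for exploratory immunogenicity methods (Section 9.6.1). Neither place assigns it safety intervals.

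Section 9.9 gives the cohort size, "Nine participants will be randomized in a ratio of 2:1 into V160 and placebo for each CMV serostatus cohort", and one precision statement. That statement supposes zero events in a V160 cell of six and concludes: "then the true incidence of that event is 46% or less with 90% confidence". The section contains no power calculation.

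**The concern.** The study tests nothing, so its numerical safety result is a set of estimated incidences. The sample-size section supports the design with an upper confidence bound, yet the analysis section asks for no bound or interval on the primary endpoint, while a secondary endpoint gets one. A table entry of 0/6 or 1/6 without an interval is easily over-read, and Section 2.1 says this study precedes one in Japanese women of childbearing age.

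All 12 V160 recipients get the same dose and schedule (Sections 4.1 and 4.3), and Section 2.1 describes the product as being developed regardless of serostatus. Sections 9.11 and 9.12 describe compliance and exposure by vaccination group or for the V160 group, without a serostatus split. The adverse events have no equally clear whole-group summary. For uncommon events, that summary is where most of the study's limited information lies.

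**Working it through.** **Inputs**
- Cohort size and allocation (Section 9.9): 9 per serostatus at 2:1, so 9 × 2/3 = 6 V160 and 9 × 1/3 = 3 placebo per cell.
- Overall (Section 4.2: "Approximately 18 participants will be enrolled in this study to include 9 CMV-seropositive and 9 CMV-seronegative individuals"): 12 V160 and 6 placebo.
- Planning statement (Section 9.9): 0 events in 6, upper bound 46%, 90% confidence, sidedness not given.
- Dropout (Section 9.1): about 20%; 9 × 0.8 = 7.2, hence 7 completers per cohort. This does not enter the 0/6 bound.

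**Reproducing the plan's own figure.** For 0 events in n, the exact upper limit solves (1 − p)^n = a, so p = 1 − a^(1/n). With n = 6:
- one-sided 90%, a = 0.10: 1 − 0.10^(1/6) = 31.9%
- two-sided 90%, a = 0.05: 1 − 0.05^(1/6) = 39.3%
- two-sided 95%, a = 0.025: 1 − 0.025^(1/6) = 45.9%

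The stated 46% matches the two-sided 95% limit. In reverse, the one-sided confidence attached to 46% is 1 − 0.54^6 = 97.5%. Other 90% two-sided methods give lower limits (Wilson 31.1%, Jeffreys 26.4%, Agresti-Coull 35.7%), so none of them accounts for 46%. A smaller denominator does not either: 0/5 at two-sided 90% gives 45.1%.

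**Zero events, per cell and pooled**

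| Group | Two-sided 90% upper limit | Two-sided 95% upper limit |
|---|---|---|
| Placebo cell, 0/3 | 63.2% | 70.8% |
| V160 cell, 0/6 | 39.3% | 45.9% |
| V160 pooled, 0/12 | 22.1% | 26.5% |

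Pooled placebo (n = 6) has the same limits as a V160 cell.

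**Non-zero counts, Clopper-Pearson two-sided 95%**
- Observed 16.7%: 1/6 gives 0.4% to 64.1%; 2/12 gives 2.1% to 48.4%.
- Observed 50%: 3/6 gives 11.8% to 88.2%; 6/12 gives 21.1% to 78.9%.

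**Chance of seeing at least one case**, 1 − (1 − π)^n. The true incidence π is an assumption, since the documents give none, and is taken as equal in both serostatus groups:
- π = 10%: 1 − 0.9^6 = 46.9% in 6; 1 − 0.9^12 = 71.8% in 12.
- π = 20%: 1 − 0.8^6 = 73.8% in 6; 1 − 0.8^12 = 93.1% in 12.

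**The case against.** The serostatus split is deliberate. It follows the primary objective, the stratified randomization (Section 6.3.2), the enrolment limit by serostatus (Section 5.2, item 19) and the sample-size statement, which is per cohort. This stands in full. A reader might infer that the absence of a pooled table conflicts with Section 9.9. It does not, because the bound there is for the six V160 recipients in one cohort.

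A reader might also infer that pooling is ruled out. The documents do not go that far. The general sentence "Incidence of AEs will be summarized as frequencies and percentages by vaccination group" could cover a pooled table, and the note "Summaries will be provided by vaccination group separately for the participants in each serostatus" is attached to Table 4. The other safety wording leans towards stratified output only, so the fair reading is that a pooled summary is not clearly specified.

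Counts are planned alongside percentages, so a reader could calculate an exact interval from them. No stopping rule or comparison depends on a safety interval, and Section 9.6.2 bases the assessment on clinical review. This limits the consequence to reporting. It does not show why the primary endpoint should lack the kind of statement used to plan it.

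Pooling is not free. It assumes similar event rates in both serostatus groups, and the 9:9 split is fixed by design. Section 2.2 cites about 71% seropositivity among Japanese mothers, so a pooled percentage describes the trial's own mix and not a population. This also stands, and is why the pooled column should be supportive.

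**Conclusion.** The point holds as a weakness of precision and reporting in a descriptive estimation study. It is not an error in a test and not an inconsistency between Table 4 and Section 9.9. No interval is named for any safety incidence, and a summary of the 12 V160 recipients is left unclear.

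A zero-event result in one V160 cell leaves a true incidence of up to 45.9% compatible with the data at two-sided 95%, against 26.5% for the pooled group; at two-sided 90% the limits are 39.3% and 22.1%. The by-serostatus limits rest only on binomial sampling with the planned denominators. The pooled limits also assume broadly similar rates across serostatus and refer to a 1:1 mix. The detection probabilities depend further on the assumed 10% or 20% incidence.

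The confidence level in Section 9.9 is a separate mismatch. It must be settled first, because a 0/12 bound at 95% placed beside a 0/6 bound labelled 90% would mislead.

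**What to change.** 1. **Section 9.9.** Correct the level attached to the 0/6 bound, state whether it is one- or two-sided, and give the 0/12 bound at that same level: 45.9% and 26.5% at two-sided 95%, or 39.3% and 22.1% at two-sided 90%. Two-sided 95% would keep the printed 46% and match the interval level in Section 9.6.1.
2. **Section 9.6.2, Table 4 and the safety row of Section 9.1.** Keep the by-serostatus tables as primary. Add exact (Clopper-Pearson) intervals at the level chosen in Section 9.9 to each primary adverse-event incidence.
3. **Table 4 and its note.** Add a supportive pooled column per vaccination group (V160 n = 12, placebo n = 6). State that it reflects the fixed 1:1 serostatus mix and assumes broadly similar event rates. Reword the note and the general sentence in Section 9.6.2 so that both say the same thing about pooling.

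The cost is a few table columns and some clarifying text, with no new data or design change. The supplemental SAP described at the opening of Section 9 can carry the analysis changes if they are made before unblinding. The one statistical cost is the homogeneity assumption behind the pooled column, and the stratified tables beside it allow any difference between serostatus groups to be seen.

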### **9.6.3 Demographic and Baseline Characteristics**

The comparability of the vaccination groups for each relevant characteristic will be assessed by the use of tables and/or graphs. No statistical hypothesis tests will be performed on these characteristics. The number and percentage of participants screened, randomized, the primary reasons for screening failure, and the primary reason for discontinuation will be displayed. Demographic variables (eg, age), baseline characteristics, primary and secondary diagnoses, and prior and concomitant therapies will be summarized by vaccination and serostatus either by descriptive statistics or categorical tables.

### **9.7 Interim Analyses**

No interim analyses are planned for this study.

### **9.8 Multiplicity**

No multiplicity adjustment is planned for this study.

### **9.9 Sample Size and Power Calculations**

Nine participants will be randomized in a ratio of 2:1 into V160 and placebo for each CMV serostatus cohort.

If a specific AE is not observed in any of the 6 participants in V160, then the true incidence of that event is 46% or less with 90% confidence.

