### **9.5.2 Safety Analysis Populations**

The All Participants as Treated (APaT) population will be used for the analysis of safety in this study. The APaT population consists of all randomized participants who received at least one vaccination and defined according to the regimen of clinical material actually received (ie, received only vaccine, or received only placebo). Participants who received a mixture of vaccine and placebo are deemed ineligible for inclusion in the APaT population. Safety data of participants ineligible for inclusion in the APaT population will be summarized in listings.

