## **9.6 Statistical Methods**

### **9.6.1 Statistical Methods for Immunogenicity Analyses**

CMV-specific NAb GMT at 1 month PD3 will be analyzed for seronegative participants using an ANOVA model. The NAb titers will be log-transformed prior to analysis. The model will include term for intervention. The treatment difference and corresponding 95% confidence interval (CI) will be estimated at 1 month PD3 on the log-transformed data. Estimates of treatment difference and corresponding 95% CI will then be back-transformed to get the GMT ratio and the 95% CI for GMT ratio. Methods related to exploratory endpoint will be described in sSAP.

Table 3 summarizes the analysis plans relating to the immunogenicity endpoints.

Table 3 Analysis Strategy for Key Efficacy Variables

Endpoint/Variable (1 month PD3)	Primary vs. Supportive Approach †	Statistical Method	Analysis Population	Missing Data Approach
Secondary				
CMV-specific NAb GMT at 1 month PD3	P	ANOVA	PPI (seronegative participants)	observed data
CMV-specific NAb GMT at 1 month PD3	S	ANOVA	FAS (seronegative participants)	observed data

† P=Primary approach, S=Supportive approach.  
ANOVA: analysis of variance, PPI:Per Protocol Immunogenicity, FAS: Full Analysis Set

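### Section 9.9 pairs a 46% upper bound with 90% confidence, but for 0 of 6 events 46% is the exact two-sided 95% limit; the mismatch is conservative

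*Combined protocol and SAP*

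**What the plan says.** Section 9.9 sets the cohort size: "Nine participants will be randomized in a ratio of 2:1 into V160 and placebo for each CMV serostatus cohort". That gives 6 on V160 and 3 on placebo in each cohort. It then takes the case where no vaccinated participant in a cohort has a given event, and concludes: "then the true incidence of that event is 46% or less with 90% confidence". It names neither the interval method nor whether the 90% is one-sided or two-sided, and no other section repeats or explains the pair.

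Three other places bear on how to read it:

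- **Section 9.5.2** defines the safety population: "The APaT population consists of all randomized participants who received at least one vaccination". Participants who stop early stay in the safety denominator, so 6 is the natural count.
- **Section 9.6.1** sets the only other confidence level in the statistical methods, for the neutralizing-antibody titer comparison: "The treatment difference and corresponding 95% confidence interval (CI) will be estimated at 1 month PD3 on the log-transformed data".
- **Section 9.6.2** plans no confidence interval for adverse events: "Incidence of AEs will be summarized as frequencies and percentages by vaccination group".

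**The concern.** A bound quoted at a named confidence level is read as the bound at that level. With no events in six people, a 90% bound should be well below 46% on either the one-sided or the two-sided reading, so either the percentage or the confidence level appears to be a slip.

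Safety is the primary objective and the study has no hypotheses. This sentence is therefore the only place where the plan puts a number on what six vaccinated participants per cohort can show about adverse-event incidence. If the pair is inconsistent, the reader does not know how much precision the sponsor meant to claim, and a study report that copies the sentence carries the inconsistency forward.

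**Working it through.** **Inputs, all from Section 9.9:** n = 6 V160 participants per cohort, 0 events, stated bound 46%, stated confidence 90%.

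**Formula.** With 0 events in n, the exact (Clopper-Pearson) upper limit is the incidence p at which the chance of seeing no events equals the tail error a. Setting (1 − p)^n = a gives p = 1 − a^(1/n). For a one-sided bound, a = 1 − confidence. For the upper end of a two-sided interval, a = (1 − confidence)/2.

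**Trying to reproduce 46% with n = 6:**

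| Reading | a | Upper limit |
|---|---|---|
| One-sided 90% | 0.10 | 1 − 0.10^(1/6) = 31.9% |
| Two-sided 90% (one-sided 95%) | 0.05 | 1 − 0.05^(1/6) = 39.3% |
| Two-sided 95% (one-sided 97.5%) | 0.025 | 1 − 0.025^(1/6) = 45.9% |

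Only the last row rounds to 46%.

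**Working back from 46%.** If the true incidence were 46%, the chance of 0 of 6 would be 0.54^6 = 0.0248. The one-sided confidence attached to 46% is 1 − 0.0248 = 97.5%. The actual one-sided error is about 2.5%, not 10%. Rounding does not matter here: any bound from 45.5% to 46.5% carries between 97.4% and 97.7%.

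**Other interval methods at 90%, n = 6, 0 events:**

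| Method | One-sided 90% | Two-sided 90% |
|---|---|---|
| Mid-P | 23.5% | 31.9% |
| Wilson | 21.5% | 31.1% |
| Wilson, continuity-corrected | 32.9% | 41.4% |
| Agresti-Coull | 25.1% | 35.7% |
| Jeffreys | 19.4% | 26.4% |
| Bayes, uniform prior | 28.0% | 34.8% |
| Poisson, −ln(a)/6 | 38.4% | 49.9% |

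None gives 46%.

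**Other denominators.** Section 9.1 mentions dropout: "Assuming a discontinuation rate of approximately 20%, 7 participants are expected to complete intervention". With n = 5 the exact two-sided 90% limit is 1 − 0.05^(1/5) = 45.1%, which rounds to 45%. Taking 20% off 6 gives 4.8, and 1 − 0.05^(1/4.8) = 46.4%. But 4.8 is not a count of people, the sentence itself says 6, and the safety population in Section 9.5.2 does not drop those who discontinue.

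**Size of the mismatch at 90%:** 46 − 31.9 = 14.1 points (one-sided) or 46 − 39.3 = 6.7 points (two-sided).

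**The case against.** The strongest reply is that the sentence is not false. A bound that holds with 97.5% confidence also holds with at least 90%, so 46% is a loose but valid inequality. That is correct, and it is why the error is conservative. It does not rescue the sentence as a statement of precision, because the purpose of naming a level is to give the bound that belongs to it.

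A second reply is that nothing depends on the figure. There are no hypotheses, no interim analysis, no prespecified criteria for stopping the study early and no planned interval for adverse events. Section 9.9 also fixes nine per cohort before giving the bound, and does not say that the size was derived from it. All of this stands. It limits the consequence to clarity and accurate reporting, and it is why the sentence is best described as the plan's only precision statement for adverse-event incidence rather than as the derivation of the sample size.

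Third, the sponsor's intent cannot be recovered from the documents. The match to the two-sided 95% limit makes that calculation a plausible source. The 95% interval in Section 9.6.1, however, concerns a titer ratio and does not settle which level was meant for adverse events. The fix therefore leaves that choice to the sponsor.

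**Conclusion.** The concern holds. The pair "46% or less with 90% confidence" is wrong as written for 0 of 6. Under the exact binomial method, 46% is the two-sided 95% upper limit (97.5% one-sided), while 90% confidence corresponds to 31.9% or 39.3% depending on sidedness. The plan understates the precision of a zero-event result by about 14 or 7 points at the level it names.

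The conclusion rests on the denominator of 6 stated in the sentence, which Section 9.5.2 supports. It does not depend on choosing the exact method, since none of the other methods checked gives 46% at 90% with n = 6. The documents do not show whether the percentage or the confidence level is the slip. The design, the sample size and the planned analyses are unaffected.

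**What to change.** Rewrite the sentence in Section 9.9 in one of two ways, and state the method and the sidedness in either case:

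- **Keep the bound.** With 0 events among 6 V160 participants, the upper limit of the exact (Clopper-Pearson) two-sided 95% confidence interval for the true incidence is 46%.
- **Keep the level.** With 0 events among 6 V160 participants, the exact upper bound is 32% at one-sided 90% confidence; or the upper limit of the exact two-sided 90% interval is 39%.

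The cost is one sentence. Nothing else in the protocol or the analysis plan has to change.
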